3.1.1 Randomization/Assignment to Study Drug

subjects with urticaria who experience acute flares while on a chronic treatment regimen or chronic spontaneous urticaria with unknown etiology at least two (2) times a week will be enrolled and randomized to receive the following treatments in each Treatment Period:

- 1 mg/100 μ L dose of ARS-1,
- 2 mg/100 μ L dose of ARS-1,
- placebo

To ensure proper wash-out between the IN doses, each subject will be randomized to one of the following sequences:

- 1 mg ARS-1 IN: placebo: 2 mg ARS-1 IN
- 2 mg ARS-1 IN: placebo: 1 mg ARS-1 IN

The side (right or left) of dosing will be alternated per randomization.

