| Statistical Analysis | 
All quantitative endpoints will be analyses using linear mixed models with fixed effects for treatment and period and a random effect for subject. For each endpoint, the following comparisons will be made using two-sided tests at the $\alpha=0.05$ level of significance:
 
 1 mg ARS-1 vs Placebo 2 mg ARS-1 vs Placebo 
There will be no adjustments for multiplicity; hence, all analyses will be viewed as exploratory and hypothesis generating, rather than confirmatory.
 |
| Study Duration | 
It is anticipated that each subject will participate in the study for up to 120 days, which comprises a 90-day screening period and 3-4-week study period during which three acute flares of urticaria symptoms will be treated.
 |
| Study Centers | 
Up to Four (4) Centers
 |

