3.0 STUDY DESIGN

3.1 Description of Study Design

This is a Phase 2, single-dose, randomized, placebo-controlled, crossover study that will consist of a screening period and an open-label treatment period. Subjects enrolled will have acute urticaria with known etiology or have chronic spontaneous urticaria with unknown etiology at least two (2) times a week while on a chronic treatment.

Each subject will be randomized to receive either a single treatment of ARS-1 (1 mg and 2 mg dose) or placebo nasal spray and then will be crossed over to receive other treatments during an acute urticaria flare. Efficacy will be primarily assessed using a patient reported pruritus/hive score and VAS for pain. Clinical assessments will also be conducted by the Investigator after dosing ARS-1.

██████████ eligible male or female subjects, 18 to 65 years of age, with urticaria who experience acute flares while on a chronic treatment regimen or chronic spontaneous urticaria with unknown etiology at least two (2) times a week will be randomized to receive ARS-1 (1 mg dose), ARS-1 (2 mg dose), or placebo. After screening subjects will return to the clinical site when experiencing an acute flare of urticaria symptoms or chronic spontaneous urticaria.

Screening Period: Subjects will be screened to assess eligibility for the clinical trial. All subjects will undergo safety screening evaluations within 90 days prior to treatment.

Open-Label Treatment Period: Subjects will return to the site when experiencing an acute flare of urticaria symptoms or chronic spontaneous urticaria before taking other acute medications. Urticaria symptoms and severity will be assessed based on both patient-reported and clinician-based assessments. After baseline safety assessments, subjects will be randomized to receive the following treatments at each of the three Treatment Periods:

- 1 mg per 100 µL dose of ARS-1,
- 2 mg per 100 µL dose of ARS-1, or
- placebo (100 µL)

If possible, rescue medication should be avoided for 15 minutes after dosing. Subjects will be monitored for both safety and symptom relief. Safety assessments will be performed after dosing and will include AEs and vital signs. Concomitant medications will be recorded.

Subjects should remain in the clinic as below:

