14.3 Efficacy Data Analyses

14.3.1 Primary Efficacy Analyses

The baseline for the primary endpoints will be the pre-dose at each visit.

Superiority comparison of ARS-1 1 mg vs. placebo and ARS-1 2 mg vs. placebo at each timepoint will be tested at the two-sided 0.05 significance level. If both ARS-1 1 and 2 mg are statistically superior to placebo, comparison between the ARS-1 doses will be conducted.

Time to effect is defined to be the time that it takes to lower one grade, two grades, and three grades.

Duration of effect is defined as the time from when the grade becomes above baseline until the grade returned to baseline.

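### Placebo is given only in Period 2 and no active dose is given there, so the planned treatment-plus-period model cannot estimate either ARS-1 versus placebo comparison

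*Combined protocol and SAP*

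**What the plan says.** Section 3.1.1 lists two sequences, "1 mg ARS-1 IN: placebo: 2 mg ARS-1 IN" and "2 mg ARS-1 IN: placebo: 1 mg ARS-1 IN", and introduces them with "To ensure proper wash-out between the IN doses, each subject will be randomized to one of the following sequences". No other sequence appears in the visible text.

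The Statistical Analysis row of the synopsis specifies "linear mixed models with fixed effects for treatment and period and a random effect for subject" for all quantitative endpoints and names two contrasts, "1 mg ARS-1 vs Placebo" and "2 mg ARS-1 vs Placebo". It makes no multiplicity adjustment and labels all analyses exploratory.

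Section 14.3.1 plans a "Superiority comparison of ARS-1 1 mg vs. placebo and ARS-1 2 mg vs. placebo at each timepoint" at the two-sided 0.05 level. It takes each visit's pre-dose value as baseline and compares the two doses with each other only if both have beaten placebo. It names no model of its own.

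Section 3.1 is looser. It describes subjects receiving ARS-1 "or placebo nasal spray and then will be crossed over to receive other treatments", without giving an order.

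**The concern.** A crossover separates treatment from visit order only if treatments change places across periods. Here the two active doses swap between Periods 1 and 3, but placebo never moves. Whatever is particular to the second visit is therefore also particular to placebo.

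The primary objective is ARS-1 against placebo, and that comparison is the one the randomisation does not protect. The comparison it does protect, 1 mg against 2 mg, is run only after both placebo tests succeed, so the testing plan cannot start as written. Software may still print a placebo contrast after setting an aliased parameter to zero. That figure would depend on the coding and would not be a treatment effect.

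**Working it through.** **Inputs.** Two sequences (3.1.1); fixed treatment and period, random subject (synopsis); 32 subjects (synopsis); two-sided 0.05 (14.3.1). Assumptions: 16 subjects per sequence, since no allocation ratio is visible; period categorical; within-subject SD σ of 0.8 points, with a range of 0.6 to 1.0, since the documents give none. The visible text has no power or effect-size figure to reproduce.

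**Step 1: estimability.** Write τ for treatment effects and P for period effects. The two sequences produce only these cell means, apart from a constant:

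| | Period 1 | Period 2 | Period 3 |
|---|---|---|---|
| Sequence 1 | τ(1 mg) + P1 | τ(placebo) + P2 | τ(2 mg) + P3 |
| Sequence 2 | τ(2 mg) + P1 | τ(placebo) + P2 | τ(1 mg) + P3 |

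Add any number k to τ(placebo) and subtract it from P2. No cell changes, so the data cannot determine τ(1 mg) − τ(placebo) or τ(2 mg) − τ(placebo). The dose difference can be read from Period 1 alone: [τ(1 mg) + P1] − [τ(2 mg) + P1].

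The full matrix confirms this. It has 32 × 3 = 96 rows and 5 columns (intercept, 1 mg, 2 mg, Period 2, Period 3):

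| Model | Rank / columns | Placebo contrasts | 1 mg vs 2 mg |
|---|---|---|---|
| Planned | 4 / 5 | not estimable | estimable |
| Plus sequence effect | 5 / 6 | not estimable | estimable |
| Subjects as fixed effects | 35 / 36 | not estimable | estimable |
| Planned, a pattern with missing periods (80 rows) | 4 / 5 | not estimable | estimable |
| Period as a linear covariate | 4 / 4 | estimable | estimable |
| No period term | 3 / 3 | estimable | estimable |

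More subjects would not help, because the aliasing holds in every row.

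**Step 2: dependence on coding.** Set the drug effect to zero and the period effects to 0, 0.3 and 0.2. If the software forces P2 = P1, the ARS-1 versus placebo estimate is 0 − 0.3 = −0.30. If it forces P2 = P3, it is 0.2 − 0.3 = −0.10. With no period term it is (0 + 0.2)/2 − 0.3 = −0.20. The same data give three answers, and the truth is zero.

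**Step 3: bias without a period term.** Each dose is given half the time in Period 1 and half in Period 3, so the bias of both placebo contrasts is (P1 + P3)/2 − P2.

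- Linear trend 0, 0.3, 0.6: 0.3 − 0.3 = 0.
- Step that persists after visit 1, 0, 0.3, 0.3: 0.15 − 0.3 = −0.15, half the shift.
- Deviation confined to Period 2, 0, 0.3, 0: 0 − 0.3 = −0.30, the full shift.

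**Step 4: false-positive rate without a period term.** The variance of each contrast is 2σ²/32 = 0.0625σ², so the standard error is 0.25σ, or 0.20 at σ = 0.8. A net deviation of 0.2 to 0.3 points is a noncentrality of 1.0 to 1.5. The two-sided t test then rejects in 16.3% to 30.7% of trials (31 degrees of freedom). At σ = 1.0 and a deviation of 0.2 the rate is 12%. At σ = 0.6 and a deviation of 0.3 it is 49% to 50%, depending on whether 31 or 62 degrees of freedom are used. The persistent step of 0.3 (bias 0.15) gives about 11% at σ = 0.8.

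**Step 5: sequences in which placebo moves.** All six orders of the three treatments with 32 subjects give rank 5 of 5. Both placebo contrasts are estimable, with variance about 0.063σ², practically the 0.0625σ² of a simple paired difference.

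**The case against.** The best defence is that the synopsis calls every analysis exploratory, that placebo was put in the middle to space the active doses, and that the middle position itself cancels any steady drift over visits. The last point is correct and matters. A reader might infer that visit-order effects pass one-for-one into the drug effect. They do so only when the deviation is confined to Period 2, and habituation or regression to the mean would tend to be monotone and partly cancel. But the plan states no linear-trend assumption, and a categorical period term does not use one.

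The exploratory label tempers the weight of a false-positive rate. It does not make a contrast estimable, and 14.3.1 still plans superiority tests. The pre-dose baseline adjusts for how severe the flare is on arrival, but not for a visit-specific response after dosing.

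The model is stated only in the synopsis, while part of 14.1 and all of 14.5 are redacted, so another model may exist. None could separate placebo from Period 2 under these sequences without an assumption about period effects.

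Two further inferences go beyond the text. The treatment period is called open-label, which might suggest that subjects know the second visit is placebo, but no visible text says what they are told. The wording in 3.1 might suggest a planned placebo-first order. It is too loose to show that and only needs reconciling with 3.1.1.

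**Conclusion.** The point stands. Under the two listed sequences and the stated model, neither ARS-1 versus placebo contrast can be estimated. This is algebraic: it needs no assumed variance, and it requires only that period is categorical, the usual reading. A few treatments given out of sequence would break the aliasing, but those rows would then carry the whole comparison.

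The false-positive figures are illustrations for an analysis without a period term. They rest on the assumed SD, equal allocation, and a Period 2 response that differs by 0.2 to 0.3 points from the average of Periods 1 and 3. The documents give neither the size nor the shape of a visit effect, so the figures do not predict the trial's error rate. Nor is the whole trial uninformative, since the dose comparison remains sound. What fails is the primary comparison as specified.

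**What to change.** Reconcile the sequences in 3.1.1 with the model in the synopsis, with 14.3.1 (which should name the model), and with the description in 3.1. There are two routes.

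1. **If the wash-out reason can be met in another way that the sponsor sets:** use sequences in which placebo is not tied to one period, for example all six orders. This keeps the planned model and needs no extra patients. It costs an amendment and a new randomisation list, and the two active doses fall in consecutive periods in four of the six orders. Whether that is acceptable is for the sponsor to settle. Six orders are an option and not a minimum: two suitable orders (1 mg, 2 mg, placebo and 2 mg, placebo, 1 mg) already give rank 5, but with a contrast variance of 0.083σ².

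2. **If the order must stay:** remove the categorical period term. State in the synopsis and 14.3.1 that ARS-1 versus placebo is confounded with visit order and rests on assuming no non-linear period effect. Replace the superiority tests with estimates and intervals, and make no superiority statement. The dose comparison should then no longer depend on the placebo tests. This costs a text change and the superiority claim.

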3.2 Study Drugs

3.2.1 Test Product

ARS-1 is a solution formulation of epinephrine intended for nasal administration.

ARS-1 will be administered by IN administration using the commercial sprayer device at a dose of 1 mg and 2 mg epinephrine per spray delivered in a volume of 100 μ L aqueous solution.

Placebo is saline to be administered by IN administration using the commercial sprayer device delivered in a volume of 100 μ L aqueous solution.

Dosing will be conducted according to the Instructions for Use (IFU) ([Appendix B](#)).

3.2.2 Dose and Dose Justification

When epinephrine is used for urticaria and angioedema, epinephrine 0.3-0.5 mg is recommended. The anticipated exposure from ARS-1 2 mg IN is similar to epinephrine 0.3 - 0.5mg IM injection products. Because the effect of epinephrine against urticaria is based on its beta 2 adrenergic effect, which is activated at a lower dose of epinephrine because of its higher affinity, a lower dose of ARS-1, 1 mg, IN will be also tested. In previous studies, doses of ARS-1 up to 2 mg IN were demonstrated to be safe in clinical studies.

3.3 Efficacy Assessments

The following efficacy assessments will be evaluated based on self-reported and clinical assessments of pruritus at pre-dose, and at 5 (± 2 min), 10 (± 2 min), 15 (± 3 min), 30 (± 5 min), 45 (± 5 min), 60 (± 10 min), 120 (± 10 min) minutes, and every 60 minutes (± 10 min) after dosing until the discharge criteria (the time when symptoms of acute urticaria have been effectively treated based on the investigator's or his/her designee's opinion will be recorded, not necessarily when subjects discharged) is met for acute flare and until urticaria symptoms returns to the baseline for chronic spontaneous urticaria. If the time to return to baseline for chronic spontaneous urticaria is beyond 4 hours, such time may be recorded by the patient and reported in the follow-up call. The actual time of the assessment and of when the symptoms return to the baseline will be recorded. Subjects should also record the date and time of recurrence, if any, of symptoms after they leave the clinic.

- A patient reported pruritus/hive score from 0 (none) to 3 (severe) for itch and hive using Uniform Assessment System (UAS) twice daily as below:

| Itch Severity Score | Amount of Itch | Itch Severity at Each Assessment |
|---------------------|----------------|--|
| 0 | None | None |
| 1 | Mild | Minimal awareness, easily tolerated |
| 2 | Moderate | Definite awareness, bothersome but tolerable |
| 3 | Intense | Difficult to tolerate |

| Hive Severity Score | Number of Hives at Each Assessment |
|---------------------|------------------------------------|
| 0 | None |
| 1 | 1-6 |
| 2 | 7-12 |
| 3 | >12 |

- Patient reported pain associated with the urticaria flare will be recorded based on a self-reported VAS score

- An investigator-rated extent of urticaria; % of body area with urticaria (Grade 1: urticarial lesions covering < 10% body surface area [BSA]; Grade 2: urticarial lesions covering 10-30% BSA; Grade 3: urticarial lesions covering > 30% BSA)
- An investigator-rated erythema score (0 = none, 1 = almost clear [slight redness], 2 = mild erythema [definite redness], 3 = moderate erythema [marked redness], 4 = severe erythema [fiery redness])

[REDACTED]

[REDACTED]

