2.0 STUDY OBJECTIVES

2.1 Study Objectives

IM epinephrine injection is indicated in the emergency treatment of allergic reactions (Type I) including anaphylaxis. Both IM and SC dosing of epinephrine is approved by the FDA as efficacious in product labeling in the US. Epinephrine injection is also recommended in medical prescribing guidelines in the US for the management of acute flares with associated angioedema in patients with urticaria. Acute urticaria is typically treated with but often unresponsive to antihistamines and corticosteroids. IM epinephrine is typically efficacious in alleviating urticarial flares. An epinephrine nasal spray (ARS-1) is being developed for patients as a needleless alternative route of epinephrine administration for the treatment of acute urticaria.

| Objective | Endpoints |
|--|--|
| Primary | |
| 
To determine the effect of ARS-1 versus placebo based on a patient reported pruritus/hive score
 
To assess time to effect and duration of effect on acute flares associated with urticaria based on a patient reported pruritus/hive score.
 | 
 • A patient reported pruritus/hive score • Patient reported pain associated with the urticaria flair based on visual analog scale (VAS) • An investigator-rated extent of urticaria; % of body area with urticaria • An investigator-rated erythema score |
| Secondary | |
| To assess the safety and tolerability of ARS-1 in subjects with urticaria after IN administration of epinephrine. | 
 • AEs • Vital signs |
| [REDACTED] | |
| [REDACTED] | |

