- Acute flare: at least 2 hours after dosing and can discharge when the discharge criteria is met (the time when symptoms of acute urticaria have been effectively treated based on the investigator's or his/her designee's opinion will be recorded, not necessarily when

subjects discharged). If no relief of pruritus symptoms after 2 hours, other acute interventions may be administered as rescue.

- Chronic spontaneous urticaria: until the urticaria symptoms returns to the baseline.

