10.5 Discharge Assessments (Treatment Periods 1 - 3)

Discharge assessments will be completed by the Investigator or his/her designee once symptoms of urticaria have been effectively treated for an acute flare or returned to baseline for chronic spontaneous urticaria. Actual time by hours and minutes will be recorded. In addition, AEs and concomitant medication will also be recorded.

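### Late return-to-baseline times in chronic spontaneous urticaria are optional in one sentence and mandatory in the next, and no visible rule covers an unreported time, so duration of effect can be biased in a direction the documents do not fix

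*Combined protocol and SAP*

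**What the plan says.** Section 2.1 lists as a primary objective "To assess time to effect and duration of effect on acute flares associated with urticaria based on a patient reported pruritus/hive score". Section 14.3.1 gives the definition: "Duration of effect is defined as the time from when the grade becomes above baseline until the grade returned to baseline". It also fixes the reference level: "The baseline for the primary endpoints will be the pre-dose at each visit".

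On how the end time is captured in CSU, the plan says four things:

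- Sections 3.3 and 6.0, for times beyond 4 hours: "such time may be recorded by the patient and reported in the follow-up call". The synopsis has the same rule inside its CSU clinic-stay instruction.
- The sentence that follows in 3.3, repeated in substance in 6.0 and in the Appendix A footnotes: "The actual time of the assessment and of when the symptoms return to the baseline will be recorded". It makes no exception at 4 hours.
- Section 3.1, on how long the subject stays: "Chronic spontaneous urticaria: until the urticaria symptoms returns to the baseline". Section 10.3 repeats this, followed by redacted text.
- Section 10.5 sets the discharge assessment at the point when symptoms have "returned to baseline for chronic spontaneous urticaria. Actual time by hours and minutes will be recorded".

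After discharge, section 3.3 adds a softer duty about relapse: "Subjects should also record the date and time of recurrence, if any, of symptoms after they leave the clinic".

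For the analysis, the synopsis applies linear mixed models to all quantitative endpoints, with treatment and period as fixed effects and subject as a random effect. It calls all analyses exploratory. No visible passage says how a missing return time is handled.

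**The concern.** Up to 4 hours, the return time can be read from scores taken at the site. Beyond 4 hours, it can depend on whether the subject notes it and passes it on by telephone. If a site reads *may* as optional, whether a duration is observed depends on how long it is. A linear mixed model fitted to the reported durations does not in general correct for that.

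The passages also leave a site with three possible readings: keep the subject until return to baseline, release the subject with mandatory recording, or release the subject with optional recording. Sites could differ, and up to four are planned. What is at stake is the size, and possibly the sign, of the ARS-1 versus placebo contrast in duration among CSU subjects.

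**Working it through.** **Nothing to reproduce.** Section 14.1 rests the sample size on practical grounds. The visible text gives no expected duration, spread, share of times beyond 4 hours or reporting rate. Only the 4-hour mark and the 32 subjects come from the documents. Every other input below is an assumption, so the figures show mechanism and range and are not a forecast.

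**Model.** Let duration T be exponential with mean m, and let c = 4 h. Times up to c are always observed. Times beyond c are reported with probability q, and unreported times are dropped. With S = exp(−c/m), the mean of the observed values is

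E = [m − (c+m)S + q(c+m)S] / [(1 − S) + qS].

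**Inputs.** ARS-1 mean 4 h: S = 0.368 and (c+m)S = 2.943. Placebo mean 2 h: S = 0.135 and (c+m)S = 0.812. The true difference is 2.0 h.

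**(a) Equal reporting under both treatments**

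| q | ARS-1 mean (h) | Placebo mean (h) | Difference (h) | Retained |
|---|---|---|---|---|
| 100% | 4.00 | 2.00 | 2.00 | 100% |
| 75% | 3.59 | 1.86 | 1.73 | 87% |
| 50% | 3.10 | 1.71 | 1.39 | 69% |
| 0% | 1.67 | 1.37 | 0.30 | 15% |

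For example, at q = 50% the ARS-1 value is (4 − 2.943 + 0.5 × 2.943) / (0.632 + 0.5 × 0.368) = 2.528 / 0.816 = 3.10 h.

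With means of 3 h and 2 h, a true 1.0 h becomes 0.68 h at 50% reporting and 0.19 h at none. With log-normal durations (log SD 0.8, means 4 h and 2 h), the true 2.0 h becomes 1.48 h and 0.59 h.

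**(b) Unequal reporting.** The treatment period is labelled open-label, so reporting could differ by treatment.

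- Placebo 30%, ARS-1 80%: 3.68 − 1.58 = 2.10 h, slightly overstated.
- Placebo 0%, ARS-1 100%: 4.00 − 1.37 = 2.63 h, overstated.
- Placebo 80%, ARS-1 30%: 2.61 − 1.89 = 0.72 h, strongly understated.
- No true difference (both means 2 h), placebo 30%, ARS-1 80%: 1.89 − 1.58 = 0.31 h, a false ARS-1 advantage of about 18 minutes.

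**(c) Censoring instead of dropping.** All times beyond 4 h were censored at 4 h and the exponential mean was estimated by maximum likelihood in simulation. The difference was 120.3 minutes against a true 120. If only some late times go unreported, this result also needs reporting beyond 4 h not to depend on how much longer the effect lasted.

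**(d) Dilution.** Suppose a fraction p of durations comes from CSU subjects, and acute flares have the same durations and are always recorded. The reporting rate in the pooled data is then 1 − p(1 − q). With p = 50% and q = 50% this is 75%, so the pooled difference is 1.73 h. With p = 50% and q = 0% it is 50%, so the difference is 1.39 h.

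**The case against.** The strongest reply is that the text does oblige recording. The mandatory sentence follows directly and has no 4-hour exception, and 10.5 requires the clock time at discharge. On that view *may* changes who records the time and where, not whether it is recorded. This is a reasonable reading and it stands as one. It is not the only reading, because the sentence specific to the late case is the permissive one. A reader might infer that late recording is simply waived; the documents do not support that either. The defect is an unresolved inconsistency.

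A reader might also infer that an ARS-1 advantage in duration is understated. That needs ARS-1 to last longer, similar reporting across treatments, and dropped values. The documents establish none of the three, and case (b) shows the sign can reverse.

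The meaning of a long time is itself unsettled. A pre-dose baseline in 14.3.1 suggests that return means wearing off. Section 10.5 places return to baseline beside effective treatment, which suggests recovery, and the definition counts time above baseline. Under a recovery reading a late time is a slow recovery and not a long benefit. Values can still go missing selectively, but their interpretation flips.

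The scope objections stand in part. The objective speaks of acute flares, and how CSU times enter it is not spelled out. The visible definition in 14.3.1 does not exclude them, and 3.3 collects them. Section 14.5, text after the CSU rule in 10.3, and parts of 3.3, 6.0 and Appendix A are redacted, so a home-scoring or missing-time rule there cannot be ruled out. In the synopsis the 4-hour sentence sits within the stay rule, so the two can be read together there.

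The exploratory status of the analyses lowers the stakes but does not settle the wording.

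**Conclusion.** The point holds as an inconsistency with a real bias mechanism. For CSU, the visible text makes late return times optional in one sentence and mandatory in the next. The stay and discharge passages show no 4-hour exit, and the visible analysis has no rule for an unreported time. Long times can therefore go missing because they are long, in a measure tied to a primary objective.

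The size is illustrative only. Under assumed exponential means of 4 h and 2 h, a true 2.0 h difference could appear as 1.4 h (50% reporting) or 0.3 h (none) if reporting is equal and missing values are dropped. Over the unequal-reporting cases tried, it ranges from 0.7 h to 2.6 h. It is close to correct if unreported times are censored. The direction cannot be stated from the documents. Only CSU subjects are exposed, so the effect on the whole trial is smaller by an amount that depends on their unstated share of the 32. The point deserves a correction, but it does not undermine the trial.

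**What to change.** 1. In the synopsis, 3.3 and 6.0, replace the permissive wording so that a return-to-baseline time beyond 4 hours *will* be recorded by the patient and collected at the existing follow-up call, identically in all three treatment periods.
2. In 14.3.1, right-censor any unreported return time at the last recorded score. Analyse duration with a time-to-event method that respects the crossover, such as a subject-stratified or frailty model, instead of dropping the value from the linear mixed model.
3. Reconcile the clinic-stay and discharge passages (synopsis, 3.1, 10.3, 10.5) with the 4-hour sentence so that sites cannot read them differently. Which stay rule applies is for the sponsor to settle.

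A home card with timed itch and hive scores would sharpen the data but is optional. If a redacted section already holds a missing-time rule, a cross-reference from 14.3.1 could replace the censoring text.

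The cost is protocol wording, minor recording by patients who leave before return to baseline, and one additional analysis model to specify and program. That last item is more than a single line of text, because the linear mixed model named in the synopsis does not handle censored times.
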